
Table 1: List of Study Endpoints

Health Endpoints	Endpoint designation
Unattended automated systolic BP 4-day average (Tues-Fri) in weeks 1 and 4	Primary study outcome (Aims 1a, 2a/2b) Study is a priori powered for this endpoint
24-hour BP levels & aortic hemodynamics	Secondary endpoints (Aims 1c & 2d)
Insulin sensitivity (HOMA-IR)	Secondary endpoint (Aims 1c & 2d)
Adrenal steroid panel (blood)	Secondary mechanistic endpoints (Aims 3a/3b)
Exposure Endpoints	
24-hr personal PM _{2.5} (filter-gravimetric mass)	Primary exposure outcome (Aims 1b, 2c)
Daily indoor PM _{2.5}	Primary exposure outcome (Aims 1b)
Black carbon, hourly personal PM _{2.5} levels	Secondary exposure endpoints

modes. In RAPIDS, no participant complained or required the AFU to be stopped due to noise³⁰. The AFUs will run in the same blinded mode continuously for the entire 4-week block. During the washout periods, the offsite investigator will

remove or install the HEPA filters in the AFUs prior to starting the next block. The HEPA filters are rated to be effective for the entire 8 weeks of active usage and will not need to be replaced.

Protocols for cardiometabolic health endpoints

Home BP: This BP measurement will be the primary outcome (Table 1). The **rationale** is that high BP is a well-established predictor of CV risk⁶⁸⁻⁷¹, the leading risk factor for global mortality³, increases due to short-term PM2.5 exposure^{5-8,36-56}, and was shown by our RAPIDS study³⁰ to be reduced by AFUs. Unattended automated BP more accurately reflects 24-hour BP, is less impacted by variability and the white coat effect and is superior to the standard technique as a predictor of hypertensive complications⁷¹. The repeat-measured morning BP average using the BpTRU device was the primary outcome in RAPIDS³⁰, thus it is important to use this same method in this renewal project.

Methods: Guidelines for BP measurement will be meticulously followed (e.g., no caffeine, exercise >1 hr prior)⁷⁰. The BpTRU device will be located in a quiet room where participants will have seated BP measured⁷¹. The proper cuff size will be fitted on their upper right arm and participants will rest seated with their feet uncrossed on floor and their arm supported at midsternal level for 5 minutes. A first BP will be determined to assure proper monitor function. Afterward, personnel will leave the room and the BpTRU will measure 5 automated unattended BP readings (1-min intervals) with the participant alone. The average of these 5 unattended BP levels and heart rates will be recorded as the endpoint for each visit. The **primary outcome** is average systolic BP (determined as above) obtained over 4 consecutive (Tue-Fri) mornings (Fig. 5). The 4-day average (not 3-day as in RAPIDS) will be used because the results showed that the BP reduction tended to become more consistent with increasing time of filtration. This will improve the stability of BP levels and increase the power for detecting changes in the primary outcome³⁰. **The 4-day average of unattended fully-automated 5-repeated BPs is a rigorous and repeatable outcome. BP will be determined fasting in the morning before participants leave the residence and prior to other factors potentially altering BP (e.g., noise, traffic, activity, outdoor temperature). This is a uniquely powerful method to capture an effect of any intervention (i.e., AFU) on lowering BP compared to using conventional clinic-based methods as done in other trials²¹⁻²⁹. This explains our unparalleled capability to detect a BP-lowering effect of AFU use (i.e., even a small - yet clinically significant - decrease in systolic BP by ~3 mm Hg as in RAPIDS)³⁰.**

24-hour BP and aortic hemodynamics: We have extensive experience with and will use the SphygmoCor XCEL PWA system which non-invasively measures upper arm BP and central aortic hemodynamics over a 24-hour period. These endpoints will all be considered secondary study outcomes. The **rationale** is that aortic BP levels differ from arm levels depending on a variety of factors (e.g., height, age, heart rate, arterial stiffness). They are validated superior predictors of CV target organ damage and future CV events⁶⁴⁻⁶⁷. Aortic BP levels also change in response to interventions (e.g., medications) and possibly to PM2.5 exposures discordant from those detected by traditional arm BP measurement. Hence, measuring aortic hemodynamic responses to AFU intervention will provide novel insight into the totality of hemodynamic responses induced by PM2.5 exposures. The device calculates aortic BPs (systolic, pulse pressure) and hemodynamics: augmentation pressure and index (AIx@75), a metric of arterial pressure wave reflection from the periphery back to the aorta and left ventricular load adjusted for a heart rate at 75 beats/min), and coronary perfusion index (CPI)⁶⁴⁻⁶⁷. These parameters are calculated by pulse wave analyses (PWA) of arterial waveforms recorded from a specialized upper arm cuff of an Oscar-2 (SunTech Medical) 24-hour ambulatory BP monitor by a mathematical generalized transfer function. PWA has been used in hundreds of studies⁶⁴⁻⁶⁷. The device will be used to determine brachial BP and aortic hemodynamics every 30 minutes over a full 24-hour period. The

rationale is that 24-hour BP levels are the “gold standard” endpoint most predictive of CV risk^{60,68,69}. They can change discordantly (e.g., white coat or masked high BP) from resting seated values⁶⁰. Finally, **nocturnal BP** is important to characterize. In RAPIDS, AFU use reduced nighttime PM2.5 exposures by the greatest extent because an AFU was situated in each participant’s bedroom (Fig. 2). Given the robust prognostic value of nocturnal BP⁶³, we will also explicitly determine the impact of AFU use on reducing PM2.5-mediated nocturnal BP elevations. **Methods:** We will follow guidelines for 24-hour BP monitoring⁶⁹ and all manuals for the SphygmoCor XCEL (<http://atcormedical.com/healthcare-professionals/>). The appropriate size cuff will be fitted on the right upper arm of participants. This cuff is connected to the BP monitor (Oscar-2) worn on a strap. The monitor will record BP every 30 minutes for a 24-hr period. Subjects will be instructed to have their right arm resting by the side of their body during each BP measurement. Instructions for troubleshooting (e.g., loose cuff) will be provided⁶⁹. Participants will record the times they went to bed and awoke to identify nocturnal periods. The data from the Oscar-2 monitor will be analyzed by the SphygmoCor system. **Outcomes:** 24-hr, daytime and nighttime averages of brachial systolic/diastolic BP, pulse pressure, and heart rates; and aortic hemodynamics (systolic BP, pulse pressure, augmentation pressure, Alx@75, and CPI).

Protocols for exposure monitoring

Indoor exposure monitoring: An indoor PM2.5 sampler will be positioned in the main room at the furthest point away from the AFU with samples being collected onto Teflon filter media using Teflon-coated aluminum cyclone sample inlets at a nominal flow rate of 16.7 L/min. This sampler will use pump systems of a type

designed and used for previous studies³⁰. These pump systems use acoustically-insulated wood cases designed for operation in home environments, minimizing pump noise. Filter samples will be collected from exposure periods starting at 8 AM on visit day 1 until 8 AM on visit day 5 during weeks 1 and 4 of each study block. For the entire duration of each block (including weeks 2-3), an indoor PM2.5 air pollution sensor (PurpleAir sensor; PA-II-SD) will be used to measure continuous PM2.5 concentrations. The PurpleAir is a low-cost, light-scattering-based PM sensor and is currently in widespread use⁷⁷. In order to ensure that the sensor performance is equivalent to the gravimetric federal reference method, a correction factor will be calculated by comparing sensor data against gravimetric filter measurements from the indoor sampler described above. The filter samples will also allow for particle characterization/source apportionment. In addition, an aethalometer (MicroAeth AE 51, Aethlabs) – used to continuously measure black carbon concentrations, provide data logging and a continuous readout – will be located near the PurpleAir sensor. **Rationale:** To determine indoor integrated 4-day, as well as daily, indoor PM2.5 and black carbon (traffic particles) during the period of health outcomes.

Personal exposure monitoring: During each 24-hr period of personal monitoring, participants will wear (on a belt or strap) a small (2 lbs) battery-powered personal particulate monitor (Thermo Scientific pDR-1500). This scientifically-validated device provides time-stamped continuous data storage of both ambient temperature and PM2.5 exposures. While time frames as brief as 5 minutes can be analyzed by the continuous data collection, we plan to evaluate 60-min exposure windows as in our prior study (Fig. 2). **Rationale:** We employed this device in RAPIDS and demonstrated the importance of characterizing time-resolved reductions in personal PM2.5 exposures, which differed from indoor PM2.5 levels due to variations in daily activity. The personal particulate monitors will be provided to the participants after visit 4 is completed and will be worn as much as possible for the ensuing 24 hours both indoors and outdoors. While sleeping, monitors will be placed on a nearby nightstand. Participants may also remove the monitor during the daytime for certain activities (e.g., showering); however, they will be instructed to keep it within close proximity. The monitor has adequate battery power to provide 24 hours of continuous monitoring. The pDR-1500 also collects sampled particles onto 37-mm Teflon filters for gravimetric and chemical analyses of PM2.5. Continuous PM2.5 data will be validated by comparing results to 24-hr integrated mass values obtained by “gold-standard” gravimetric measurements of filters. Using continuous exposure windows in addition to 24-hr filter-based measurements will allow for a shorter time frame resolution of intra-day exposures and for characterizing hourly exposure reductions achieved by the AFU (Fig. 2).

Activity log: During each 24-hour period of personal monitoring, participants will be asked to keep a log of specific activities: sleep/awake time, outdoor windows open, time outdoors, and time in traffic. They will also keep a log during the entire study to record: open window times, exercise, nights spent outside their residence.

Filter analysis: Sample handling, processing, and analysis will take place in a Class 100 ultraclean room at the Michigan State University Exposure Science Laboratory. Gravimetric determinations of PM2.5 mass will be made using a microbalance (XP6UD5, Mettler Toledo) in a temp/humidity-controlled room as described elsewhere^{30,31}.

Protocols for blood outcomes

Blood draws collection: On week 4/visit day 5 (Blocks 1-3) after BP measurement, an experienced investigator will draw fasting blood from the participant's antecubital fossa using clean universal precautions. We will draw 10 ml of blood each time, which will also allow for stored aliquots for post hoc studies. We will obtain blood for steroidomics profiling at the designated time points from as many participants as possible. Missing any blood collection may weaken our final power to meet aim 3; however, it will not impact eligibility for participants to remain in the study as it will not adversely affect the main study objectives (Aims 1 and 2).

Comprehensive steroidomic profiling: The HPAA is highly responsive to stressors such as air pollution, as we herein hypothesize. The *rationale* for focusing on HPAA activation as a central mechanism of PM2.5-induced cardiometabolic effects has been addressed (Fig. 1)³². We will measure ACTH levels (a metric of central nervous system hypothalamic/pituitary activation) by the MDRC clinical laboratory. [name] has performed extensive work to develop comprehensive steroid profiling using liquid chromatography-tandem mass spectrometry (LC-MS/MS)⁷⁸⁻⁸⁷. By simultaneously measuring multiple steroids across several adrenal pathways, we can identify patterns and biomarkers for stress-responses, including aldosterone⁸⁷, steroid sulfates and 11-oxyandrogens as biomarkers of acute and chronic HPAA activation. Among the advantages of LC-MS/MS is the capacity to interrogate multiple adrenal steroids, including mineralocorticoids, cortisol, and 11-oxygenated steroids (glycercerhetic acid-like factors)⁸⁶ that inhibit 11 β -hydroxysteroid dehydrogenases and thus potentiate the hypertensive effect of cortisol. Our unique LC-MS/MS method allows us to uncover the full extent of adrenal pathway activation contributing to hypertension via multiple mechanisms with unprecedented biochemical sensitivity and specificity from a small blood sample (<0.25 mL of serum) and measures up to 35 steroids (Table 2). In this panel are multiple parent steroids, hybrid steroids and steroid precursors that possess glucocorticoid and mineralocorticoid activity. Synthesis and release of all or some of these steroids can increase due to stress responses (multiple potential pathways elicited by PM2.5 exposure)³² and play a key mechanistic role in promoting both pro-hypertensive responses and metabolic insulin resistance³². **Methods:** Aliquoted serum samples will be stored in a -80°C freezer for annual batched analyses. For steroid analysis, serum samples (0.1 mL) are mixed with internal standards and collected via supported-liquid extraction, resolved by 2-dimensional chromatography (Agilent 1260 and 1290 binary pump systems), and measured using multiple reaction monitoring with an Agilent 6495 triple quadrupole LC-MS/MS operating in positive electrospray ionization mode as described⁷⁹⁻⁸⁴. The Delta-5/5 α -Panel is analyzed as oxime derivatives, and steroid sulfates are analyzed in negative ion mode^{79,83}. Cortisol in saliva and hair is extracted with methanol and measured as above⁸⁵. Thus, we will perform a comprehensive assessment of HPAA activity, and the benefits of AFU usage, across several biologically important timescales. This includes a disruption in diurnal rhythm which alone can cause adverse effects (11PM saliva cortisol), as well as subacute HPAA (serum ACTH and steroidomics panel) and chronic HPAA activation (hair cortisol) induced by PM2.5.

Table 2. Steroid panels using LC-MS/MS

Delta-4/Estrogens Panel (0.1 mL)	Delta-4/Estrogens Panel (0.1 mL)	Delta-5/5 α - Panel (0.1 mL)	Steroid Sulfate Panel (0.01 mL)
Cortisol Precursors	Cortisol, Cortisone, & Hybrid Steroids	
Pregnenolone17OH-PregnenoloneDehydroepiandrosteroneAllopregnanolone5α-Pregnane-3β,17β-diol-20-oneAndrosteroneDihydrotestosterone	
Pregnenolone Sulfate17OH-Pregnenolone SulfateDehydroepiandrosterone Sulfate5-Androstenediol SulfateAndrosterone Sulfate

Progesterone11OH-Progesterone16OH-Progesterone17OH-Progesterone11-Deoxycortisol21-Deoxycortisol	
Cortisol*Cortisone*18OH-Cortisol*18-oxo-Cortisol*		
	Androgens & Precursors		
	
Androstendione		

Mineralocorticoids/ Precursors	
 • Testosterone • 11OH-Androstenedione • 11Keto-Androstenedione • 11OH-Testosterone • 11Keto-Testosterone 	
 • Etiocholanolone Sulfate
• 11-Deoxycorticosterone*		
• Corticosterone*		
• 18OH-Corticosterone*		
• Aldosterone*		
• Estrogens		
• Estrone		
• Estradiol		

Bio-banked blood: We will store 0.5-ml aliquots of serum and plasma at the end of each study block. We have access to a -80°C freezer with alarms and backup power in our research room at the University of Michigan Cardiovascular Medicine outpatient clinical facility at Domino's Farms Lobby A. This will allow for post hoc analyses of many possible biomarkers after study completion depending upon the nature of our results.

Study Pitfalls and Remediation Plans

We do not anticipate difficulties successfully completing this trial or utilizing the methods proposed as they have all been performed in our laboratories and many have been conducted in our previous clinical trials (e.g., RAPIDS). It will be critical to maintain robust recruitment and retention of subjects. We plan to further reinforce mutually beneficial relationships that have already been established with residents and facility staff and address concerns about the study on an ongoing basis (e.g., townhall meetings). We will adopt and modify the study (as long as it does not compromise the science) if deemed required by community feedback during the start-up period in year 1 and during the study if such a need arises. Other pitfalls are described in individual subsections.

Outreach Activities and Knowledge Dissemination

A social ecological approach⁸⁸ will be used to translate the findings of the study into health-promoting actions that can be taken by older adults, family caregivers, housing managers, health care providers, and policy makers to reduce the health risks of exposure to air pollution in congregate housing for the elderly. Common values of community-based health promotion include:

- Stakeholder engagement in the design and evaluation of translation strategies^{89,90}
- A comprehensive evaluation of process, implementation, and sustainability⁹¹
- A dissemination plan⁹⁰

Evaluation strategies applied to the health education materials and methods will include process evaluation, assessment of short term learning outcomes, and a six-month follow-up on the extent of adoption and maintenance of behavioral or environmental changes among selected housing communities. Evaluation criteria for selected target audiences (housing managers; community-based network) will address standards of utility, feasibility, propriety, and accuracy (fidelity)⁹⁰. The study team will:

1. Consult with study participants and key stakeholders throughout the study to help develop the strategies and media for educating older adults and providers of housing for the elderly.
2. Conduct tailored, one-to-one educational sessions with study participants to share results and implications, and to develop educational materials and methods.
3. Design and conduct communications to address potential mobility, cognitive, and sensory limitations of older adults (e.g., access to group meetings; impaired vision and hearing), and health literacy.
4. Develop and evaluate fact sheets in cooperation with the Residents' Council and Activities coordinators for distribution through existing channels (e.g., meetings, flyers).

5. Schedule meetings for presentations by study team members⁸⁹ to the residents, staff and key associates.
6. Utilize the network of community-based organizations and advocacy groups⁹² to reach the larger population of managers of senior housing communities, health care providers and policy makers via presentations at professional meetings. Key dissemination networks include marketing and networking trade meetings of senior housing providers; the Area Agencies on Aging, and the Michigan Association of Homes and Services to the Aging.
7. Disseminate findings for broader application by health professionals through channels of peer-reviewed publications and presentations at conferences on aging.

Statistical Analyses and Data Management

Sample size, power considerations, and statistical analysis plans are provided in full in the Study Record: the PHS Human Subjects and Clinical Trials Information document.

Project Management and Schedule

As described in the multiple PI leadership plan, Drs. [name] and [name] together will provide oversight of the entire project. Since the proposed research is interdisciplinary and involves multiple schools/departments, a governance structure will be implemented in order to ensure effective management and coordination. The proposed research will follow a work plan that will meet the milestones shown in the “Study Timeline” attached to the Study Record: the PHS Human Subjects and Clinical Trials Information document. We will hold bi-monthly general project meetings involving all staff and investigators to present the latest data and to coordinate study logistics and analysis. The team of investigators on this proposal is well-poised to integrate their various disciplines and ensure a high probability of success for accomplishing the proposed specific aims.

DATA MANAGEMENT AND STATISTICAL CONSIDERATIONS

Study Power and Analysis Plans:

With 50 subjects randomized to blocks 2 (“bedroom alone AFU”), and (“control”) in a random sequence, we anticipate adequate power using our proposed cross-over study design for observing significant reductions in **average systolic BP (primary endpoint)**. With the repeated BP measurements collected in this cross-over design, we will do paired analysis for power calculations, since each subject can serve as their own control given sufficient washout periods and because we have a priori pre-specified the group comparison hypothesis for each aim clearly beforehand. We will be able to achieve 90.3% power in **Aim 1a** for detecting a 3 mm Hg in mean systolic BP difference comparing the “bedroom AFU” to the “control” group at both the acute (4-day) and chronic (4-week) time periods, assuming that the standard deviation (SD) of systolic BP is 8.2 mm Hg. The detectable mean difference of systolic BP between “bedroom FU” vs “control” with the corresponding statistical powers that we can achieve is as follows:

Detectable mean BP difference between “active intervention” vs. “control” (Hg)	2.4 mm	2.6 mm	2.8 mm	3 mm Hg	3.2 mm	3.4 mm
Statistical Power	75.4%	81.9%	86.1%	90.3%	93.6%	95.4%

Within the range of the SD of systolic BP measurements from 6.2 to 9.8, the statistical power for aim 1a we can achieve ranges between 72.1% and 97.5% to detect a 3 mm Hg change in mean systolic BP. Similar powers will be achieved for **Aim 2a** as well, comparing “bedroom alone AFU” (block 2) versus “control” (block 3) group. In our previous AFU study (RAPIDS, see: Progress Report) we observed a 3.2 mm Hg reduction in systolic BP by active versus control intervention. Therefore, the pre-specified effect size (3 mm Hg systolic BP reduction) for which we have designed this renewal proposal to have adequate power to observe is well justified. The study is a priori designed and

powered to determine the pre-specified outcomes in aims 1a, 2a, and 2b. Other comparisons evaluated in aims 1b (24-hr personal-PM_{2.5} exposures); 1c (secondary health endpoints); 2c (24-hr personal-PM_{2.5} exposures); 2d (secondary health endpoints); as well as in aims 3a (differences in steroid levels between blocks) and 3b (mediation analyses) are all deemed secondary study outcomes. We will collect the data as proposed and analyze the results using the same statistical methods as outlined for the primary study outcomes. However, since these are secondary endpoints only (i.e., hypothesis generating results), we will analyze the data for trends and for “nominal” statistical significance. We will also not perform a priori power calculations for all secondary endpoints.

Both the primary endpoints and the secondary measures such as diastolic BP, 24-hour BP levels and HOMA-IR will be reported as mean (median) \pm SD (IQR). One-sample paired t-test will be performed to compare each outcome variable between active intervention group and the control group. In case there are extreme values or that the variables are not normally distributed, Wilcoxon signed-rank test, a non-parametric test for comparing repeated measurements' mean ranks, will be performed for robustness¹. When the distribution of an outcome variable is not anticipated to follow a normal distribution, we will transform it to meet normality assumptions as best as possible before we fit regression models to adjust for confounders (age, sex, BMI, dose of BP tablets, type of BP control medication). Non-parametric correlation coefficients, such as Kendall's tau⁷ or spearman's rho⁸, between the principal outcomes and exposure measures will be calculated at each time point. Such measures provide robust inferences. Multiple hypothesis testing will be adjusted through the Holm's procedure⁹.

More specifically, to adjust for other confounders, we will use linear mixed models²⁻⁴ to evaluate the effect of interventions on the outcomes (e.g. BP levels) adjusting for confounders. The mixed models will fully represent the structure of the data by taking into account the within-subject correlations of the outcome variables measured repeatedly at different time points over the study design. We will also evaluate the impact of other variables that may impact the results. To be more specific, a mixed effect model with a random intercept and a random slope²⁻⁴ will be fit for the longitudinal measurement of the outcomes: $Y_{ij} = a_0 + a_1 t_{ij} + a_2 I(B_{ij} = 1) + a_3 I(B_{ij} = 2) + a_4 X_{ij} + b_{i0} + b_{i1} t_{ij} + e_{ij}$, where Y_{ij} denotes the repeated average BP outcomes for subject i at occasion j , B_{ij} denotes what intervention is subject i randomized to at occasion j , and X_{ij} are the other covariates that would be controlled in the model (age, sex, BMI, dose of BP tablets, type of BP control medication). So in **Aim 1a**, we hypothesize $a_2 \neq 0$ and test for $H_0 : a_2 = 0$, and in **Aim 2a**, we hypothesize $a_3 \neq 0$ and test for $H_0 : a_3 = 0$, and in **Aim 2b**, we are testing $a_2 = a_3$. Similar models will be fit for other secondary outcome variables, such as ABPM, HOMA-IR, etc. When it happens some outcome variables have inflated zero measures, we will adopt zero-inflated regression models or a two-part mixture regression (tobit) model^{5,6} on the outcome changes between “active intervention” vs. “control”.

Other statistical considerations:

Missing data: We will try to avoid missing data when collecting data through the study design. When missing data happens, we will test if the data are missing completely at random (MCAR). If it is MCAR or the amount of missing data is less than 10%, analysis will be performed based on the complete data. If the amount of missing data is more than 10%, multiple imputations (5-10 times) will be utilized through mi package in R¹⁰. The analysis will be performed on each imputed data set, and later merged through mitools package in R¹¹. Multiple imputations are based upon the missing-at-random (MAR) assumption¹². Sensitivity analysis¹³ will be examined when inferences depart from the MAR assumption.

Data Monitoring and Coordination: The Data Coordinating Center (DCC) at U-M will ensure the proposed research collect and manage data in a confidential and secure manner. U-M DCC will review data to control its data quality and integrity, organize data using uniform formats and vocabulary to facilitate analysis and document protocols for collecting, filtering and formatting the data. All files stored at the U-M database will be managed by [name] as was done previously for other successful grants. The database provides a central location for disseminating and retrieving study information, including codebooks, common data element definitions, synopses of studies, data collection forms (if necessary), and analyses in progress. We will create and maintain a webpage for any distributed software packages, with detailed documentation as well as contact information. We will also archive all relevant publications from the proposed research by following the law of copyrights.

Quality Management Plan: All study outcomes have been performed by our research team in prior studies and are well-established research endpoints using in hundreds of prior experiments. We will follow the developed protocols used in our prior experiments and established manual of operations ([name], available on request). All proposed blood outcomes will be measured in accredited clinical laboratories. We will plan regular (quarterly) group meetings during the trial to identify and mitigate any unanticipated study pitfalls that develop during the trial.

Bibliography & References Cited

1. [name] RD, Rajagopalan S, Pope CA III, [name] JR, Bhatnagar A, Diez-Roux A, Holguin F, Hong Y, Luepker, RV, Mittleman M, Peters A, Siscovich D, Smith SC Jr, Whitsel L, Kaufman JD. Particulate matter air pollution and cardiovascular disease. An update to the scientific statement from the American Heart Association. *Circulation* 2010; 121: 2331-78.

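### Neither analysis named for the primary outcome has a block (period) term: the paired t-test ignores a block shift, and the mixed model's undefined time term may or may not absorb one

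*Combined protocol and SAP*

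**What the plan says.** All of this is under Study Power and Analysis Plans.

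- **Power.** It rests on a paired comparison: "we will do paired analysis for power calculations, since each subject can serve as their own control". The inputs are 50 participants, a 3 mm Hg difference, an SD of systolic BP of 8.2 mm Hg and a stated power of 90.3%. The two conditions are given "in a random sequence"; no ratio or method of balancing the sequences is stated.
- **First analysis.** "One-sample paired t-test will be performed to compare each outcome variable between active intervention group and the control group", with the Wilcoxon signed-rank test as the robust alternative.
- **Second analysis.** To adjust for confounders, the plan fits "a mixed effect model with a random intercept and a random slope" and writes the Aim 1a null hypothesis as a zero coefficient for the first intervention indicator. The fixed effects are a linear time term, two intervention indicators, and age, sex, BMI, and dose and type of BP medication. The time variable is not defined as study time or as time within block.

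No block, period or sequence term appears in either analysis, and the two are not ranked. The Protocol Modifications change how BP is measured but do not restate the analysis.

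**The concern.** In a two-period crossover, anything that moves everyone's BP between Block 1 and Block 2 enters the active-minus-sham difference with opposite signs in the two sequences. The modified protocol makes such a shift plausible. Participants measure their own BP with a device delivered on day 1, first readings are due on day 2, and there is no run-in. Any familiarisation effect therefore falls mainly in Block 1 for everyone.

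Block and sequence are known for every participant, so the shift can be removed almost for free. Left in, it costs power and makes the estimate depend on how evenly the two orders happen to be filled. Because neither analysis is named as primary and time is undefined, a reader cannot tell how much protection the final result will have.

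**Working it through.** **Inputs.** From the plan: n = 50, target effect 3 mm Hg, SD 8.2, two-sided alternative (the hypothesis is written as a non-zero coefficient), BP in weeks 1 and 4 of each block with a one-week washout (study weeks 1, 4, 6 and 9 in the Protocol Modifications schedule). Assumed, because the documents do not give them: alpha 5%, a common block shift π of 3 or 5 mm Hg, and simple 1:1 randomisation of sequence where stated.

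**1. The plan's own power.** If 8.2 is the SD of the paired difference, SE = 8.2/√50 = 1.160, noncentrality = 3/1.160 = 2.59 and power is 71.8%, not 90.3%. If 8.2 is the SD within each condition and the correlation is 0.70 (assumed), the paired SD is 8.2 × √(2 × 0.30) = 6.35 and power is 90.6%. The stated 90.3% thus implies a paired SD s of about 6.4. I carry both s = 6.4 and s = 8.2.

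**2. What a shift does to the paired t-test.** With true effect τ, the mean difference is τ + π in one sequence and τ − π in the other. The overall mean is τ + π(n₁ − n₂)/n. At 25/25 the shift cancels and the true SE stays at s/√50 (0.905 for s = 6.4). The SD that the t-test estimates grows to about √(s² + π² × 50/49):

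- s = 6.4: √(40.96 + 9.18) = 7.08 for π = 3; √(40.96 + 25.51) = 8.15 for π = 5
- s = 8.2: √(67.24 + 9.18) = 8.74; √(67.24 + 25.51) = 9.63

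Simulated power of the t-test for 3 mm Hg:

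| s | Sequences | π = 0 | π = 3 | π = 5 |
|---|---|---|---|---|
| 6.4 | exactly 25/25 | 90% | 86% | 77% |
| 6.4 | simple randomisation | 90% | 84% | 72 to 73% |
| 8.2 | exactly 25/25 | 72% | 67% | 59% |
| 8.2 | simple randomisation | 72% | 66% | 58 to 59% |

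At 25/25 the test is conservative: type I error is about 3.1% (π = 3) and 1.3 to 1.4% (π = 5) for s = 6.4. Averaged over simple randomisation it stays near 5%.

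**3. Unequal sequences.** At 29/21 the estimate is off by (29 − 21)/50 = 0.16 times the shift: 0.16 × 3 = 0.48 and 0.16 × 5 = 0.80 mm Hg. That is 16% and 27% of the 3 mm Hg target. For Binomial(50, 0.5), the probability of a split of 29/21 or worse is 0.32. When the imbalance works against the effect, t-test power at s = 6.4 is about 71% and 46%.

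**4. What the mixed model's time term does.** These are least-squares results with a separate intercept per person and no random slope, at 29/21 and π = 3; c = 0.16.

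- Time = study week, one occasion per block: time and block are the same variable, so the bias is 0.
- Time = study weeks 1, 4, 6, 9: deviations from the mean are −4, −1, 1, 4, with sum of squares 34 and cross-product with block 5. The bias is cπ(34 − 25)/(34 − 25c²) = 0.48 × 9/33.36 = 0.13 mm Hg.
- Time = week within block (1, 4, 1, 4): cross-product 0, so the full 0.48 mm Hg remains.

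**5. With a block term.** The estimate is the average of the two sequence means, so π cancels. SE = (s/2)√(1/n₁ + 1/n₂), with 48 df.

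| s | 25/25 | 29/21 |
|---|---|---|
| 6.4 | SE 0.905, power 90% | SE 0.917, power 89% |
| 8.2 | SE 1.160, power 72% | SE 1.175, power 71% |

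These hold for any size of common shift.

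**The case against.** The strongest reply is that the plan is not a bare t-test. The Aim 1a hypothesis sits in a mixed model with a time term, and with one occasion per block and time coded as study week that term is a block indicator in all but name. This stands. A reader might infer that the plan's sole or primary test ignores period; the documents do not support that, because they do not rank the two analyses. But they do not define time either, and step 4 shows the protection ranging from complete to none.

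A reader might also infer that a block shift biases the trial. It does so only given the split that occurs: randomised order makes the error average zero, and the t-test keeps its 5% level over simple randomisation. Nor does the estimate become noisier at an exact 25/25 split; only its estimated standard error does.

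The Washout period section reports no significant order effect in the earlier trial and BP back to baseline within a week. That is some reassurance, mainly about carryover. It comes from 3-day interventions with staff-run BpTRU readings, and a non-significant test does not show absence of an effect.

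Finally, season is a weak argument for a block term. With rolling enrolment, seasonal shifts differ between participants in size and direction, and a common block factor would not remove them. Familiarisation with self-measurement is the better case.

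**Conclusion.** The point holds in a limited form. The plan names two unranked analyses of the primary outcome, neither with a block term, and one has a time variable whose coding decides whether a common block shift is removed. The trial would not be invalid: at equal sequences the t-test is unbiased and merely conservative, and over randomisations it is valid.

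What is at stake is avoidable loss. At a paired SD of 6.4 mm Hg, t-test power falls from 90% to 86% and 77% for shifts of 3 and 5 mm Hg at 25/25, and at a 29/21 split there is an error of 0.5 to 0.8 mm Hg in an unpredictable direction. Period-adjusted power stays near 89 to 90% (71 to 72% at SD 8.2).

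The shift sizes, the SD of 6.4, the 5% alpha and simple randomisation are assumptions. The structure of the result does not depend on them, but its size does, and a small shift would cost little.

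**What to change.** Name one primary analysis: a linear mixed model with fixed effects for condition, block (as a factor) and week within block, and random effects for person and person-by-block. With one value per block, the equivalent is to compare the block differences between the two sequences. Keep the paired t-test and the Wilcoxon test as supportive analyses. If a linear time term is retained anywhere, define it.

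This needs only a change of SAP wording and no new data. It costs one degree of freedom: essentially no power at 25/25, and about 1 percentage point at 29/21 if there is no shift. It will not correct seasonal shifts that differ between participants.

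Balancing the sequences by permuted-block randomisation would also help, but it is a separate change to the allocation procedure. It may come too late for some participants, since the Protocol Modifications already refer to experience with subjects in 2021. The block term is useful either way.
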